Changes in immune homeostasis that predict relapse following dose reduction are most likely to be identified at the site of inflammation. The distinctive molecular changes that underlie the loss of immune homeostasis prior to relapse can be identified by studying gene expression changes in colonic tissue, as has previously been done to predict response to infliximab treatment¹⁵. We wish to compare gene expression changes between patients who remain symptomless on the lower dose of tofacitinib with those patients who ultimately show clear clinical signs of relapse. We expect that the differential gene expression (DEG) list may contain negative regulators of cytokine signaling (SOCS proteins) and/or inhibitors of STAT proteins (PIAS proteins), whose activity critically regulates the functional activation of STAT proteins and downstream cytokine induced gene expression. These studies will identify genes that can be used as biomarkers for relapse following tofacitinib dose decrease and also help in identifying genes that can be more rapidly screened in blood for the purpose of predicting relapse in patients in the clinic.

NHS Foundation Trust

4: Using immune monitoring of the mucosal immune system to identify biomarkers of relapse and remission.

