7.1 Study Design

This is a prospective observational study. We will prospectively enroll a cohort of 50 UC patients who have achieved an adequate response to tofacitinib at a dose of 10mg bd and whose dose is being reduced to 5mg bd following a routine flexible sigmoidoscopy. Colonic

tissue and blood samples will be collected at study entry, and patients' disease course will be followed-up through routine care.

Week 44 has been chosen for the primary endpoint, as 44 weeks post dose de-escalation was used as the endpoint in OCTAVE Sustain.

Primary endpoint:

• Biomarkers, clinical markers and histological markers associated with ongoing treatment with 5mg bd in the absence of steroids at week 44.

Secondary Endpoints

• Biomarkers, clinical markers and histological markers associated with steroid free endoscopic remission at routine endoscopy at week 44

Biomarkers / outcome measures will include:

- Clinical status (SCCAI)
- CRP and faecal calprotectin (as part of routine care)
- Histological markers of disease activity (Nancy histological index) (as part of routine care)
- STAT activation in peripheral blood mononuclear cells
- Cytokine expression in peripheral T cells
- Gene signatures in colonic biopsies

Guy's and St Thomas' MHS

NHS Foundation Trust

Flow Diagram

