For genetic studies, RNA will be prepared using Qiaprep microRNA kit, then quantified on a Qubit instrument and 2ug RNA will be sent for library preparation and RNA-sequencing using commercial genomic services at Novogene. Briefly, mRNA is purified from total RNA using poly-T oligo-attached magnetic beads, then isolated mRNA is fragmented, reverse transcribed and stranded libraries will be prepared and sequenced using the Illumina platform to generate at least 20M reads per sample. Bioinformatic analysis of the RNA sequencing data will be carried out at Novogene as part of the service package and will provide comprehensive gene expression analysis. Unsupervised and supervised clustering analysis will be performed to provide a high-level view of the differences between the two groups analysed and to produce a differential gene expression (DEG) list. Enrichment analysis of the DEGs will be performed using the clusterProfiler software for enrichment analysis, including GO Enrichment, DO Enrichment, KEGG and Reactome database, to predict biological functions or pathways are significantly associated with DEGs. The top 5-10 genes from the DEG list will be validated by quantitative real-time PCR using RNA from mucosal tissue and also from PBMC and T cells isolated from peripheral blood. In addition, obtained biopsies will be defrosted and processed either by:

- 1. A whole tissue digestion protocol
- Placed in culture to allow crawl out of lymphocytes as previous described (Di Marco Barros Cell 2016)
- 3.

The resulting single cell suspension will either be analysed by flow cytometry (in the presence/absence of stimulation) or processed for transcriptomic analysis. Further, a single biopsy will be placed into RNAlater and subsequent RNA/DNA extraction performed. The resulting material will be saved for genotyping, gene expression analysis and T/B cell receptor analysis.

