13.2 Data handling and record keeping

Pseudo-anonymised patient data will be kept on a password-locked computer. Every patient will be appointed a two-digit study number. All patient specific data will be recorded using only this number. The full name and birth date will only be recorded on the informed consent form. The study coordinator will monitor patient inclusion and protocol steps, coordinate data entry, perform data analyses and reporting. Data will be double entered into a Microsoft Excel spreadsheet to endure validity and quality.

All trial data will be stored in line with the Data Protection Act (1998). Records will be retained for a maximum of 7 years.

14 Statistical considerations

14.1 Sample size calculation (some pilot/feasibility studies may not require a formal sample size calculation)

Given the endpoints are exploratory, sample size calculations are not possible.

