14.2 Statistical analysis

[name], clinical research fellow in gastroenterology, will perform the statistical analyses.

Baseline variables will be presented as either mean and standard deviation or medians and inter quartile range, depending on the normality of the data.

Receiver operator curves will be generated to determine optimal cut-offs for continues variables, predictive of disease flare.

Kaplan-Meier curves will be generated to allow comparisons of subdivisions of patients based on genetic and biochemical variables, using determined cut-offs.

Univariate and Multivariate analyses will be performed on clinical, biochemical and genetic variables to establish predictors of disease flare.

15 Ethical considerations

This is a non-interventional, observational study. Approvals will be sought from REC and HRA. Patients will need to provide informed consent to participate, and the only data collected from patients which occur in addition to standard of care are the additional tissue and blood samples collected at baseline and at week 44 for genetic, immune cell and cytokine analyses. Decisions regarding patient's care will have no relation to the study and will be directed by the patient's care team. Data collection and monitoring will occur in accordance with the rules and regulations set out above. The study design, management, undertaking, analysis and dissemination of results have had patient involvement, via a patient representative who sits on our project approvals board.

16 Financing and Insurance

Guy's and St Thomas' NHS Foundation Trust will take primary responsibility for ensuring that the design of the study meets appropriate standards and that arrangements are in place to ensure appropriate conduct and reporting are adhered to. King's College London as co-sponsor also provides cover under its No Fault Compensation Insurance, which provides for payment of damages or compensation in respect of any claim made by a research subject for bodily injury arising out of participation in a clinical trial or healthy volunteer study (with certain restrictions).

17 Reporting and dissemination

It is intended that the results of the study will be reported and disseminated at international conferences and in peer-reviewed scientific journals. A manuscript of the final study results will be submitted to an IBD specific journal (IBD or JCC) or to the IBD section of a general gastroenterology journal (Gut, Gastroenterology or CGH).

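### qPCR of the top 5-10 genes in the cohort that selected them confirms the assay, not the prediction, and does not support the claim of usable relapse biomarkers

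*Protocol*

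**What the plan says.** Section 7.1 gives the only source of patients: "We will prospectively enroll a cohort of 50 UC patients". Section 8 places recruitment at a single centre. The protocol mentions no second cohort, hold-out set, external data set or resampling.

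Section 5, question 3, gives the comparison, which sets patients without symptoms against those who relapse: "We wish to compare gene expression changes between patients who remain symptomless on the lower dose of tofacitinib with those patients who ultimately show". Section 10.3 applies clustering analyses to the two groups "to produce a differential gene expression (DEG) list" (the DEG list). The qPCR step follows: "The top 5-10 genes from the DEG list will be validated by quantitative real-time PCR using RNA from mucosal tissue". The same sentence adds blood cells as a second source of RNA.

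Section 5, question 3, states the intended conclusion: "These studies will identify genes that can be used as biomarkers for relapse following tofacitinib dose decrease". Section 14.2 uses genetic variables again in the same cohort: "Univariate and Multivariate analyses will be performed on clinical, biochemical and genetic variables to establish predictors of disease flare". Genetic markers are part of the primary objective in section 6. Section 14.1 says: "Given the endpoints are exploratory, sample size calculations are not possible".

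**The concern.** The DEG list ranks genes by how well they separate relapsers from non-relapsers in these patients. With thousands of genes and 50 patients, some of that separation is chance. A second assay on the same people inherits the same chance imbalance, because neither the people nor their outcomes have changed. Agreement between RNA-seq and qPCR therefore shows that expression was measured well. It says nothing about whether the association would appear in other patients.

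The claim is at stake. A reader who sees genes described as validated, beside a promise of usable biomarkers, will take it that prediction has been tested. The plan as written contains no such test. Section 5 also says predictors would help decide who stays on the higher dose, so an overstated gene signature would matter beyond this study.

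**Working it through.** **No figure to reproduce.** The protocol gives no sample size calculation, alpha, power or expected performance for the gene signature. The check is how often genes with no predictive value would pass the qPCR step.

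**Input from the protocol:** 50 patients; top 5-10 genes; qPCR in mucosa and in blood cells.

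**Assumptions, not in the protocol:** 20,000 independent genes, none predictive; 15, 20 or 25 relapses; genes ranked by two-sample t-test with no false discovery filter; a gene passes qPCR at two-sided p < 0.05; correlation r between RNA-seq and mucosal qPCR in the same sample of 0.7 to 0.95; correlation between mucosa and blood of 0 to 0.5. Section 10.3 does not say whose RNA is used. That it is the same patients' is inferred, because no other source is described.

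**Hand calculation.**
1. Null genes expected at p < 0.05: 20,000 × 0.05 = 1,000.
2. A middle gene of the top ten has rank 5.5, so p = 5.5/20,000 = 0.000275. On 48 degrees of freedom that is |t| = 3.93. The gene's correlation with relapse status is 3.93/√(3.93² + 48) = 0.493.
3. A second measurement with correlation r to the first has an expected correlation with relapse of about 0.493r = c, so t ≈ c√48/√(1 − c²), with standard deviation about √(1 − r²). The critical value is 2.01.
   - r = 0.7: c = 0.345, t = 2.55, SD = 0.714. Pass = Φ((2.55 − 2.01)/0.714) ≈ 0.77.
   - r = 0.9: c = 0.444, t = 3.43, SD = 0.436. Pass = Φ((3.43 − 2.01)/0.436) ≈ 0.999.
   - blood, 0.3: c = 0.148, t = 1.04, SD = 0.954. Pass = Φ((1.04 − 2.01)/0.954) ≈ 0.15.
4. Apparent AUC ≈ Φ(t√(1/n₁ + 1/n₂)/√2). With 20 relapses and 30 non-relapses the root is 0.289. At r = 0.7: Φ(0.736/√2) = 0.70. At r = 0.9: Φ(0.990/√2) = 0.76. The true value is 0.50.

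**Simulation** (25 runs per setting, top 10 genes, null throughout; range over 15, 20 and 25 relapses):

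| RNA-seq/qPCR correlation | Null genes passing mucosal qPCR | Mean apparent AUC |
|---|---|---|
| 0.7 | 76-77% | 0.70-0.72 |
| 0.8 | 88-96% | 0.72-0.76 |
| 0.9 | 99-100% | 0.75-0.79 |
| 0.95 | 100% | 0.78-0.79 |

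A repeat with fresh draws gave 70-78% at 0.7 and 99-100% at 0.9, with AUC about 0.69-0.78. Taking the top 5 instead of the top 10 at r = 0.9 gave 100%.

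| Other material | Null genes passing |
|---|---|
| Blood, same patients, mucosa-blood correlation 0 | 4% |
| Same, 0.2 | 8-14% |
| Same, 0.3 | 16-17% |
| Same, 0.5 | 36% |
| 50 independent patients | 4-8% |

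Only the independent patients bring the pass rate back to about the nominal 5% whatever the correlations. Even there, the chance that at least one null gene passes is 1 − 0.95⁵ = 22.6% for 5 genes and 1 − 0.95¹⁰ = 40.1% for 10, so a later validation study would need a multiplicity-adjusted criterion.

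**Effect of a false discovery filter.** With a 5% Benjamini-Hochberg rule the list was non-empty in 0-16% of runs per setting (about 5% expected). Under a complete null, such a rule would usually send nothing to qPCR.

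**The case against.** **It is a laboratory term.** In a section on sample analysis, validation by PCR can simply mean checking a sequencing result on a second platform. The western blot step in the same section is described as confirming the flow results, and section 14.2 never treats qPCR as a test of prediction. This is fair. A reader might infer that the study will announce genes validated as predictors, but no sentence says so. The ambiguity matters because section 5 promises usable biomarkers and the protocol offers no other test of the genes.

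**The blood arm is a real filter.** It stands that most chance mucosal hits would fail in blood if the two tissues correlate weakly. A reader might therefore overread the 99-100% figure: it describes mucosa only, at high assay correlation, with no filter. The blood arm still uses the same patients and outcomes, so passing it is not independent validation.

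**A false discovery threshold may exist elsewhere.** It may, and its absence from the protocol is not a finding. So chance genes *could* appear confirmed; it does not follow that they *will*. A threshold does not remove the problem when some signals are real, because the selected genes' apparent performance is still inflated by selection.

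**The study is exploratory.** Section 14.1 uses that word, section 5 hypothesises cautiously, and section 15 separates care decisions from the study. This lowers the severity. It does not temper the biomarker sentence in section 5.

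**Tissue time point.** Because biopsies are also taken at flare and week 44, a reader might infer that flare tissue will be set against week-44 tissue, which would find genes of active inflammation. The protocol does not specify that contrast. Section 5 defines baseline as the point of dose reduction and speaks of changes before relapse. What stands is narrower: question 3 and section 10.3 do not name the time point of the gene comparison.

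**Conclusion.** The point holds in a limited form. As described, qPCR in the single 50-patient cohort is technical confirmation of the sequencing result and cannot show that the genes predict relapse. The section 5 statement goes further than the design can support.

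The size depends on assumptions outside the protocol. If none of 20,000 independent genes were predictive and no filter were applied, about 70-78% (assay correlation 0.7) to 99-100% (0.9) of the selected genes could pass mucosal qPCR, with an apparent AUC of roughly 0.7 to 0.8. These figures show what the step cannot exclude. They do not forecast this study's results. The conclusion does not depend on a particular correlation in the range examined.

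This should be fixed before analysis. It concerns wording and how performance is estimated; recruitment, sampling and patient care are unaffected.

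**What to change.** 1. Section 10.3: replace *validated* with *technically confirmed*. Keep that word for independent patients and a prespecified, multiplicity-adjusted criterion.
2. Section 5, question 3: say that the studies *will nominate candidate genes for independent validation*.
3. State that the predictive relapse comparison uses baseline biopsies, taken at dose reduction. Analyse flare and week-44 tissue separately and label it descriptive.
4. Report the gene signature's predictive performance only from cross-validation or a bootstrap that repeats gene selection inside every resample.
5. If both rectal and sigmoid samples are sequenced, handle the within-patient correlation with a random effect or equivalent. Relapse status is constant within a patient, so a fixed patient block would make the relapse contrast inestimable.

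Adjustment for the baseline Nancy index should not be compulsory. The index is itself a candidate marker, and forcing it in changes the question to added value beyond histology.

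**Cost:** edits to two passages, one clarifying sentence and resampling code on data the study will generate anyway. Reported performance will be lower, and the claim becomes one of candidate genes.

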10.4 Sample Storage Procedures

Plasma samples will be stored in a -80 degrees Celsius upright freezer. Biopsy samples will be stored in a 4 degrees Celsius fridge for short term storage prior to processing, and RNA extracted from these samples will be frozen in a -80 degrees Celsius upright freezer. PBMC samples will be stored in a temperature monitored nitrogen vapour tank (≤-175 degrees

Celsius). All storage units are located in the Dept. of Immunobiology, SIMS, [name], Guy's Hospital, KCL.

10.5 Data Recording/Reporting

The Chief Investigator will act as custodian for the trial data. The following guidelines will be strictly adhered to:

- Data will be kept in site files/trial master file and will be stored and protected to the standards described in GSTFT and King's College London Information Security Policy and the Data Protection Act.
- Data will be accessed by named researchers only, on password protected, encrypted computers. If data needs to be transferred between the two hospital sites of the same trust (Guy's and St Thomas' Hospitals), it will be on encrypted media and GSTT laptops. Data will be transferred via secure GSTFT email to other GSTFT email.
- If written communication between researchers is required between GSTFT and KCL, secure email with NHS.net accounts to NHS.net accounts will be used.
- Data will be accessed by named researchers only, on password protected, encrypted computers. If data needs to be transferred between the two hospital sites (Guy's and St Thomas' Hospitals), it will be on encrypted media and GSTT laptops. If written communication between researchers is required, secure GSTFT email will be used to other GSTFT email, or NHS.net accounts to NHS.net accounts.
- Data will be pseudoanonymised. A unique study ID will be given to each participant for use in the research database. A password protected Microsoft Excel file will be used to create a database. Access to the secure file linking study ID with personal details will be held on a separate, password-protected NHS computer on an NHS server.
- All study data will be kept in a secure office for clinical research staff at Guy's & St Thomas' Hospital. Only members of the medical and research team with the adequate security clearance will have access to the office. They will also be kept as safe as possible from other damage such as fire or water damage.

10.6 Sample Receipt/Chain of Custody/Accountability

- Study samples will be labelled with patients' study number only at the point of collection, and transported to the laboratory via standard internal measures.
- A record of all samples will be made at the point of collection and upon arrival at the laboratory.
- Upon arrival to the laboratory the physical integrity of the sample will be assessed. If this has been compromised, the study teams and sponsor will be informed.

10.7 Sample Transfer to sites outside the Organisation

In the study, blood and colonic tissue will be collected from patients in accordance with the patient consent form and patient information sheet and shall include all tissue samples or other biological materials and any derivatives, portions, progeny or improvements as well as all patient information and documentation supplied in relation to them. Further, the custodian of the Materials and use the Materials for the Study only. For the avoidance of doubt Recipient shall only use the Material in accordance with the consent provided by the Study

Donors (if applicable) and shall always use the Materials with dignity and respect and shall always use good laboratory practice in handling Materials.

The blood and colonic tissue will be appropriately sent to [name], dept. of Immunobiology, SIMS, [name], Guy's Hospital, KCL for STAT activation, cytokine analysis, and genetic analysis of the samples to be carried out in accordance with the analytical plan agreed with the Chief Investigator.

[name], dept. of Immunobiology, SIMS, [name], Guy's Hospital, KCL will process, store and dispose of blood and colonic tissue in accordance with all applicable legal and regulatory requirements, including the Human Tissue Act 2004 and any amendments thereto. While Provider uses reasonable endeavours to ensure the quality of the Materials, the Materials are provided 'as is' and it makes no representation and gives no warranty or undertaking in relation to the Materials, including but not limited to its safety, fitness for purpose or use of any kind.

The blood and colonic tissue will not be transferred to any party not identified in this protocol and are not to be processed and/or transferred other than in accordance with the patients' consent. After ethics approval for the study has expired, the blood and colonic tissue will be disposed of in accordance with the Human Tissue Act 2004, and any amendments thereto, or transferred to a licensed tissue bank.

Stool samples will be collected by the patient, given to a member of the direct care team and will be sent to Pathology services (Viapath) at St Thomas' Hospital. This is required as part of standard of care and no additional specimens are needed for this study.

11 Assessment of Safety

General safety assessments will be made as part of each clinical assessment, as per standard of care by the treating team. These will include clinical history and examination, blood tests, faecal tests, endoscopy and imaging, at the treating team's discretion. Specifically, disease flare, complications of immunosuppression (ie. Infection or malignancy) and specific tofacitinib side effects (ie. Vascular thromboembolism) will be observed for. As per standard of care, patients will be informed about potential adverse events and encouraged to contact our helpline email address should concern arise.

GSTT is the Sponsor and KCL is a co-sponsor, and the SAE is related (that is, it resulted from administration of any of the research procedures), to the study procedures or is an unexpected occurrence (that is, the type of event is not listed in the protocol as an expected occurrence) then it must be reported immediately upon knowledge of the event to R&D and always within 24 hours. For all other AEs these must be reported to GSTT when copied into the Annual Progress Report.

Important Medical Events (IME) & Pregnancy

Events that may not be immediately life-threatening or result in death or hospitalisation but may jeopardise the patient or may require intervention to prevent one of the other outcomes listed in the definition above should also be considered serious.

Guy's and St Thomas'

Although not a serious adverse event, any unplanned pregnancy will also be reported via the SAE reporting system.

